8.2 Treatments administered

8.2.1 Methods of assigning subjects to treatment groups

The study is planned as a multicenter study. At the study baseline visit (V2), subjects will be randomized to treatment groups stratified by site. Randomization in blocks of appropriate size and blockwise distribution of the IP to the study sites ensure an approximately correct ratio of 2:1 of enrolled subjects in the two treatment groups per site and overall. The block size will not be disclosed to investigators until the study is unblinded.

No other criteria for stratification of randomization will be applied.

Randomization will be done by using an IWRS.

At the Cycle 2 baseline visit (V8) of the bilateral treatment period, all eligible subjects will receive open-label NT 201.

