12.1 Determination of sample size

The results of the previous study [Jog 2017, Merz Pharmaceuticals GmbH 2017] suggest that a treatment effect of about one standard deviation might be expected. Assuming a 5% type I error and a randomization ratio of 2:1 a total sample size of 51 analyzable subjects is required to achieve 90% power. In order to account for uncertainty in parameter estimates and drop-outs it has been decided to randomize approximately 75 subjects.

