Descriptive statistics for metric variables will be number of values analyzed (n), number of missing values (nmiss, if any), number of imputed values (nimip, where applicable), mean, standard deviation (SD), median, quartiles, minimum, and maximum. Mean, quartiles, and median will be reported to one decimal place more than the data were collected, for the SD two decimal places more will be displayed; for calculation of derived variables, the number of decimal places is given in the sections below and the number of decimal places to be displayed for descriptive statistics of metric derived variables is defined in [Appendix 8.7](#). For both collected and derived data, descriptive statistics for changes from study / Cycle 2 baseline, as applicable, will be displayed with the same number of decimal places.

⁶ including important and non-important PDs

Frequency tables for qualitative variables will be absolute and percent frequencies (n, %). Frequency tables will include the number of missing values, where applicable. If not specified otherwise, calculation of percentages will be based on all subjects from a specified population and treatment group with non-missing data at the respective visit. The denominator will be specified in a footnote to the tables for clarification if not otherwise obvious. Percentages will be reported to one decimal place.

If not otherwise specified, statistical tests will be conducted 2-sided at type I error rate 5%. P-values will be reported to four decimal places (e.g., $p=0.0375$). P-values below 0.0001 will be presented as '<0.0001'. Confidence intervals (CIs) will be 2-sided for 95% confidence level.

The last valid value before first administration of the investigational product (IP) will be analyzed as study baseline and the last valid value before IP administration in Cycle 2 will be analyzed as Cycle 2 baseline, but only considering data from Cycle 2 baseline visit (V8) and from control visit at Week 18 of Cycle 1 (V7).

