  LSMEANS TRT01P / pdiff=control('C1 Placebo') CL alpha=0.05;
  REPEATED / group=trt01p;
  WHERE avisit eq 'Week 6 (V4)' and param eq 'Angular tremor amplitude at
  wrist level dominant UL: Task with maximum amplitude at study baseline';
RUN;
```

Here, “TRT01P” denotes the randomized treatment group, “SITEID” the study site, “CHG” the change from study baseline to Week 6 (V4) in maximum tremor amplitude measurement at wrist level [RMS deg] during the unilateral treatment period (i.e., the primary endpoint, derived as described above), and “BASE” maximum tremor amplitude measurement at wrist level at study baseline (derived as described above).

The following statistics will be displayed:

- n (number of values analyzed)
- p-values of fixed class effects and the fixed continuous covariate
- LS Means of each treatment group (including standard error [SE] and 95% CI)
- LS Mean treatment difference (including SE, 95% CI, and t-test p-value).

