4.1.1.2 Sensitivity Analyses

If not specified otherwise, the exploratory sensitivity analyses described in the following will be performed on the FAS-UP (OC). Study sites might be pooled for statistical analysis to overcome convergence issues in ANCOVA models. Prior to unblinding, the need of pooling was only seen for sensitivity no. 2 (see below and Section 4.7.3).

- *Sensitivity analysis no. 1:* The ANCOVA model specified in Section 4.1.1.1 will be repeated on the PPS (OC).
- *Sensitivity analysis no. 2:* For the analysis of the treatment-by-pooled site interaction, study sites from the United States of America [USA] and Canada will be grouped together (“North American [NoA] sites”) and compared vs. all remaining study sites from Poland (“Polish [Pol] sites”). The ANCOVA model specified in Section 4.1.1.1 will be modified as follows to estimate treatment effects by pooled study site: The fixed effect study site will be replaced by fixed effects for pooled study site [NoA vs. Pol] and the treatment-by-pooled study site interaction. Apart from the respective modifications in the MODEL and LSMEANS statement, the SAS code will be identical to the one provided in Section 4.1.1.1. LS-Means by treatment group and LS Mean treatment differences will not only be provided overall but also by pooled study site (NoA vs. Pol).⁸
- *Sensitivity analysis no. 3:* Gender⁹ (as fixed class effect) and age (as fixed continuous covariate) will be added to the model specified in Section 4.1.1.1. The SAS code will be similar to the one provided there, with the only modification that gender⁹ and age will be added to the MODEL statement and gender⁹ additionally to the CLASS statement. The same statistics as those specified in Section 4.1.1.1 (with p-values for all fixed class effects and the fixed continuous covariates in the model) will be displayed.
- *Sensitivity analysis no. 4:* In case more than 10% missingness on the primary efficacy endpoint occurs in either treatment group among all treated subjects, multiple imputation of missing maximum tremor amplitude measurements at wrist level at study baseline and at Week 6 (V4)^{10,11} will be performed and results for the primary efficacy endpoint from an ANCOVA

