4.1.2.2 Other Secondary Efficacy Endpoints

Other secondary endpoints are defined in Section [2.2.1.2.2](#). TETRAS based endpoints will be derived analogously as described in Section [4.1.2.1](#) for the two key secondary efficacy endpoints (see also [Appendix 8.1](#) for assignment of TETRAS items to the different TETRAS scores). This requires that answers to all respective items are available. No missing value replacement will be performed for any other secondary efficacy endpoint. Inferential statistical results reported for other secondary efficacy endpoints will be interpreted only descriptively.

Unilateral treatment period:

Other secondary endpoints of the unilateral treatment period will be analyzed by applying ANCOVA models similar to that for the primary analysis of the primary endpoint (see Section [4.1.1.1](#)). However, for TETRAS subscales, the study baseline of the analyzed TETRAS (subscale) score will be used for baseline adjustment. For GICS by investigator and GICS by subject, the study baseline of the TETRAS ADL subscale score will be used for baseline adjustment. The same statistics as defined in Section [4.1.1.1](#) will be reported.

Furthermore, descriptive statistics for metric variables will be provided by treatment group.

Bilateral treatment period:

Other secondary endpoints of the bilateral treatment period all belong to Category A, (see Section [4.1](#)). They will be analyzed by applying ANCOVA models similar to that for the primary analysis of the primary endpoint (see Section [4.1.1.1](#)). However, the Cycle 2 baseline of the analyzed variable will be used for baseline adjustment.

Since all subjects will receive the same active treatment (NT201) in Cycle 2, it is not intended to test the effect of treatment for any other secondary endpoint from the bilateral treatment period.

Rather, the above mentioned ANCOVA models will be used to estimate the average changes from Cycle 2 baseline by LS Means and respective 95% confidence intervals.

SAS code similar to the statements provided in Section [4.1.1.1](#) will be used. Only the LSMeans statement will be adapted as follows because the LS Mean treatment difference is not needed:

```
LSMEANS TRT01P / OM CL alpha=0.05;
```

The following statistics will be displayed:

- n (number of observations used in the analysis)

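### Sensitivity analysis no. 2 drops study site, the only randomisation stratum, although pooling the interaction does not require it, and leaves the weights of its overall difference unstated

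*SAP*

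**What the plan says.** - **Randomisation.** Protocol 8.2.1: "subjects will be randomized to treatment groups stratified by site". The same section rules out any other stratification factor.
- **Primary model.** SAP 4.1.1.1 fits treatment, site and baseline, with separate residual variances by treatment group and Kenward-Roger degrees of freedom. Its LS means line is "LSMEANS TRT01P / pdiff=control('C1 Placebo') CL alpha=0.05".
- **Sensitivity analysis no. 2.** SAP 4.1.1.2: "The fixed effect study site will be replaced by fixed effects for pooled study site [NoA vs. Pol] and the treatment-by-pooled study site interaction". It adds: "LS-Means by treatment group and LS Mean treatment differences will not only be provided overall but also by pooled study site". Apart from changes to the MODEL and LSMEANS statements, the code is to match the primary code. The changed statements are not printed.
- **Reason given.** Footnote 8 of the SAP cites convergence, given many sites and few subjects, and dates the decision before unblinding. SAP 4.1.1.1 and 4.7.3 record that no pooling was needed for the primary model.
- **Reach.** SAP 4.1.2.1 applies the same analysis to both key secondary endpoints. SAP 4.6.3 names it as the only planned subgroup analysis.
- **Status.** SAP 4.1.1.2 treats all sensitivity results as exploratory and descriptive.
- **OM option elsewhere.** The Cycle 2 code in SAP 4.1.2.2 reads "LSMEANS TRT01P / OM CL alpha=0.05".

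**The concern.** The analysis changes two things at once: it adds a treatment-by-region interaction and it removes the randomisation stratum. If its result departs from the primary result, the reader cannot tell which change caused this.

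Removing site also moves any between-site variation within a region into the residual. Randomisation targets 2:1 within each site, so the treatment contrast barely feels that variation, but its standard error is charged for it. The regional confidence intervals and the interaction are what this analysis exists to show, and they would look less precise than the design makes them.

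Separately, an overall difference in a model with an interaction depends on how the two regions are weighted, and the SAP does not say how. Two programmers could follow the text and report different overall figures.

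**Working it through.** **1. The plan's own figure.** Protocol 12.1 assumes "a treatment effect of about one standard deviation might be expected" and concludes that "a total sample size of 51 analyzable subjects is required to achieve 90% power". A two-sample t-test (noncentral t, two-sided 5%, 2:1, effect 1 SD) gives 89.2% power at 16 + 32 = 48 and 91.0% at 17 + 34 = 51. The 51 is reproduced, and nothing below changes it.

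**2. Does convergence require dropping site?** Residual degrees of freedom with 75 subjects and 15 sites (Protocol 6.1 and 12.1), common variance, no baseline term:
- primary (intercept, treatment, 14 site effects): 75 − 1 − 1 − 14 = 59;
- site kept plus treatment-by-region (the region main effect lies within site): 59 − 1 = 58;
- as written (intercept, treatment, region, interaction): 75 − 4 = 71.

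The baseline covariate takes one more from each. The site main effects are already fitted in the primary model, so the pooled interaction adds a single parameter to it.

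**3. Effect of dropping site.** The documents give neither the regional split nor the between-site SD. Assumptions: 20% of subjects in Poland, residual SD 1, blocks of 3 within site, between-site SD τ from 0 to 0.75. There were 3,000 simulated trials per scenario with no treatment effect. The simulation has a common residual variance and no baseline covariate, so it simplifies the planned model. For the overall difference as written, with 50:50 regional weights:

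| τ | mean model SE | empirical SD | ratio | null rejection |
|---|---|---|---|---|
| 0 | 0.308 | 0.311 | 0.99 | 5.3% |
| 0.32 | 0.321 | 0.313 | 1.03 | 4.2% |
| 0.5 | 0.340 | 0.317 | 1.07 | 3.6% |
| 0.75 | 0.377 | 0.321 | 1.17 | 2.1% |

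With site kept and the same 50:50 weights, model SE and empirical SD are 0.311 and 0.317 at τ = 0.5, and 0.312 and 0.316 at τ = 0.75, so the SE is about the right size. The regional differences were not tabulated separately. They use the same residual, so they err in the same direction.

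**4. Effect of the weights.** Let w be the Polish share, with equal precision per subject. The SE of a 50:50 contrast relative to one weighted by observed shares is 1/√(4w(1 − w)):
- w = 10%: 1/√0.36 = 1.67
- w = 20%: 1/√0.64 = 1.25
- w = 30%: 1/√0.84 = 1.09
- w = 40%: 1/√0.96 = 1.02
- w = 50%: 1.00

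The targets differ only if the effects do. With w = 20% and effects of 1 SD in North America and 0.5 SD in Poland, share weights give 0.8 × 1 + 0.2 × 0.5 = 0.90 and equal weights give 0.75. With effects of 1 and 0 the values are 0.80 and 0.50. With equal effects, including zero in both regions, the targets coincide.

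**5. The two sources separated.** Mean 95% CI half-widths at w = 20%, τ = 0.5:
- primary model: 0.497
- site kept, observed-share weights: 0.497
- site kept, 50:50 weights: 0.623
- as written, 50:50 weights: 0.678

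Of the total widening of 0.181, the weighting accounts for 0.623 − 0.497 = 0.126 and the loss of site for 0.678 − 0.623 = 0.055.

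**The case against.** - **The analysis decides nothing.** It is exploratory and descriptive. The primary analysis supplies the overall effect and this model is meant to supply the regional ones. That stands, and it is why loss of power or of significance is not a fair measure of harm here.
- **Pooling was foreseen.** Protocol 12.4.1.1 allows sites to be pooled, with details set under blind conditions, and this was done. That stands for the choice to pool. It does not supply a reason for removing main effects that the primary model fits unpooled.
- **No bias, and a conservative error.** With 2:1 targeted in each site, dropping site should add little or no bias, and null rejection falls rather than rises. That also stands. The harm is imprecision and unclear attribution.
- **The size may be nil.** At τ = 0 the SE is correct. With τ = 0, 13 sites and a near-even split, the analysis as written is slightly narrower than the primary (half-width 0.490 against 0.498).
- **A stronger reading is tempting.** A reader might infer that the overall difference is fixed at 50:50, and so tests a different null with intervals that are too wide. The documents do not support this. LSMEANS is one of the two statements the SAP says will change, so 50:50 is only what the SAS default would give, and the Cycle 2 code shows that the authors use OM in places. The nulls part only when regional effects differ. The wider interval from equal weights is correct for that contrast.

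**Conclusion.** The point holds as a low-cost improvement to an exploratory analysis. Site, the only randomisation stratum, leaves the model without a reason that requires it. If sites differ within region, the standard errors are overstated. For the overall difference under 50:50 weights this is about 0%, 7% and 17% at a between-site SD of 0, 0.5 and 0.75 residual SDs, given an assumed 20% Polish share and the simplified model above. The true split and site variance are not in the documents, so the actual figure could be nil.

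The weighting is an omission to fill, not an error shown. Under the SAS default the SE of the overall difference would be about 1.25 times that of a share-weighted one at a 20% Polish share, and equal at 50%. The confirmatory test, alpha and sample size are unaffected.

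**What to change.** For the primary and both key secondary endpoints, keep site nested in region:

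`MODEL CHG = TRT01P REGION SITEID(REGION) TRT01P*REGION BASE / solution ddfm=kr;`

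Retain the same REPEATED statement. Report the regional treatment differences and the interaction estimate, each with its 95% CI. If site is still to be dropped, say why.

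Secondary: print the modified LSMEANS code and state the regional weights, preferably observed margins, so that the overall figure can be read beside the primary estimate. An ESTIMATE statement with the weights written out would leave nothing to a default.

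Cost: a few lines of code, a sentence in the SAP and no new data. The model uses one residual degree of freedom more than the primary (58 against 59 in the count above), and 13 more than the analysis as written (58 against 71). If sites do not differ, the price is small: at τ = 0 and a 33% Polish share, the half-width with observed weights is 0.500 with site kept and 0.489 without. If the blind has already been broken, add this as a labelled extra analysis beside the planned one.

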4.1.1.1 Primary analysis

The primary efficacy endpoint is based on assessments of angular tremor amplitude [deg] for the motor-dominant UL at study baseline⁷ and Week 6 (V4) with standardized computerized kinematic analysis using the TremorTek® device. At each visit, these assessments are performed for four tasks, repeated in three assessments rounds (for further details, please refer to CSP Section 9.1.1.2.1). From these data, the primary efficacy endpoint will be derived as follows:

- The maximum angular tremor amplitude at wrist level will be computed in the following three steps at study baseline (defined at beginning of Section 4):
 1. For each of the four tasks and each of the three assessment rounds, individual 20-second recordings from a kinematic sensor will yield three angular tremor amplitude values in deg for flexion/extension, radial deviation/ulnar deviation and for pronation/supination levels and a single combined Root Mean Square (RMS) angular tremor amplitude value. The RMS will be calculated as (rounded by five decimal places):

$$RMS = \sqrt{\frac{x_1^2 + x_2^2 + x_3^2}{3}},$$
 where
 - x_1 = angular tremor amplitude for flexion/extension [deg]
 - x_2 = angular tremor amplitude for radial deviation/ulnar deviation [deg]
 - x_3 = angular tremor amplitude for pronation/supination [deg]
 2. Calculation of the arithmetic mean from the three assessment rounds of the combined RMS for each of Tasks I to IV [RMS deg], separately for each task (rounded by five decimal places).
 3. Among Tasks I to IV selection of the task with the maximum arithmetic mean calculated during Step 2. The amplitude of this task [RMS deg] will be considered for the primary endpoint.

⁷ For definition of study baseline see beginning of Section 4.

- For the selected task (see Step 3), the angular tremor amplitude at wrist level at Week 6 (V4) [RMS deg] will be derived analogously, i.e., as arithmetic mean of the combined RMS (see Steps 1 and 2 above) based on the respective data from V4.
- Change from study baseline to Week 6 [RMS deg] will be calculated by subtracting the maximum angular tremor amplitude at wrist level at study baseline from the respective value at Week 6 (V4), derived as described above.

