Derivation of maximum tremor amplitude at wrist level at study baseline (as defined at beginning of Section 4) according to Steps 1 to 3 (see above) is only meaningful if the three angular tremor amplitude values for flexion/extension, radial deviation/ulnar deviation and for pronation/supination levels are each available for all four tasks from all three assessments rounds. Likewise, maximum tremor amplitude at wrist level at Week 6 (V4) can only be calculated as described above if the three above-mentioned angular tremor amplitude values are each available for the selected task from all three assessment rounds. If any of these study baseline or Week 6 (V4) data are missing, the primary endpoint cannot be derived and will be considered as missing. Under the assumption of missingness at random (MAR), missing values will not be replaced for the primary analysis.

The confirmatory analysis of the primary efficacy endpoint will be based on the FAS-UP (OC) using least square means (LS Means) from a baseline-adjusted analysis of covariance (ANCOVA) as implemented in SAS PROC MIXED. Fixed class effects will be the treatment group (NT 201 versus placebo) and study site. Study baseline angular tremor amplitude at wrist level for the task with the maximum amplitude will be the fixed continuous covariate. Variances will be allowed to differ between treatment groups. Denominator degrees of freedom will be calculated according to the Kenward-Rodger method.

The difference in LS Means between treatment groups with associated 95% CI from this model will serve as an estimate for the size of the treatment effect. The two-sided t-test of the LS Mean treatment difference will be applied to the following testing problem at $\alpha_{2\text{-sided}}=5\%$:

$$H_0: \mu_{NT201} - \mu_{Placebo} = 0 \quad \text{vs.} \quad H_1: \mu_{NT201} - \mu_{Placebo} \neq 0,$$

where $\mu_{NT201} - \mu_{Placebo}$ denotes the expected mean treatment difference on the primary efficacy endpoint, with a negative difference indicating a treatment effect in favor of NT 201.

In case of convergence issues, study sites might be pooled for statistical analysis. Prior to unblinding, no need of pooling was seen for the primary analysis (see also Section 4.7.3).

SAS code similar to the following statements will be used:

```
PROC MIXED data = dataset;
  CLASS TRT01P (REF='C1 Placebo') SITEID;
  MODEL CHG = TRT01P SITEID BASE / solution ddfm=kr;

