⁸ In the CSP, a model “with treatment-by-site interaction to estimate treatment effects by site” was planned, with the option to pool sites for statistical analysis and the statement that “the necessity and details of pooling will be determined under double blind conditions”. To avoid convergence issues due to the high number of study sites in relation to the number of subjects to be analyzed, it was decided prior to unblinding to pool sites (NoA sites vs. Pol sites) for this interaction analysis. This adaption is thus not considered as a change from analyses planned in the CSP.

⁹ Standard name for variable is ‘sex’ in CDISC SDTM/ADaM.

¹⁰ Note that in case the task with maximum amplitude at wrist level at study baseline cannot be derived due to missing or incomplete assessments of tremor amplitude at wrist level at study baseline, the respective value at Week 6 (V4) cannot be derived either and hence needs to be imputed as well, even if TremorTek measurements of angular tremor amplitude at wrist level are completely available at Week 6 (V4) or not.

¹¹ Maximum tremor amplitude at V3/V4 to be calculated for the task with maximum tremor amplitude at study baseline.

model (as described in Section 4.1.1.1) applied to 1000 completed datasets will be combined for statistical inference. This analysis will be performed on all subjects treated in Cycle 1.

In detail, the following four steps will be performed:

1. One thousand completed datasets will be generated using the FCS statement with the regression method for arbitrary missing data patterns in SAS PROC MI. Variables considered will comprise maximum tremor amplitude at wrist level from previous visits¹², treatment, study site, gender⁹ [female/male], and age [years]. SAS code similar to the following will be used:

```
PROC MI DATA=dataset SEED=602011079 NIMPUTE=1000 OUT=mi_
  MINIMUM=. . . 0 0 0
  ROUND= . . . 1 1 1;
WHERE avisit="Week 6 (V4)" and param="Angular tremor
amplitude at wrist level dominant UL: Task with maximum
amplitude at study baseline";
CLASS SITEID SEX TRT01P;
FCS REG(BASE = TRT01P SITEID SEX AGE);
FCS REG(V3VAL = TRT01P SITEID SEX AGE BASE);
VAR TRT01P SITEID SEX BASE V3VAL AVAL;
RUN;
```

where SITEID = study site
SEX = gender
TRT01P = randomized treatment group
AVAL = maximum tremor amplitude at wrist level at Week 6 (V4)¹³
V3VAL = maximum tremor amplitude at wrist level at Week 4 (V3)¹³
BASE = study baseline value for maximum tremor amplitude at wrist level

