2. The primary endpoint will be calculated from observed and imputed maximum tremor amplitude at wrist level at study baseline and at Week 6 (V4) in the completed datasets.
3. For each completed dataset, the primary endpoint will be analyzed by an ANCOVA model as defined in Section 4.1.1.1 whereby “ods output diffs=diff_mi LSMeans=lsm_mi” will be added to the SAS code.
4. The results from the 1000 imputed datasets will be combined for statistical inference using PROC MIANALYZE. SAS code similar to the following will be used:

¹² including study baseline value for imputation of missing values at Week 4 (V3) and study baseline and Week 4 (V3) values for imputation of missing values at Week 6 (V4).

¹³ calculated using measurements for the task with maximum tremor amplitude at study baseline

```
PROC MIANALYZE data=diff_mi;  
  MODELEFFECTS estimate;  
  STDERR stderr;  
  ODS OUTPUT ParameterEstimates=DIFF_MIAN;  
run;  
  
PROC MIANALYZE data=lsn_mi;  
  BY treatment;  
  MODELEFFECTS estimate;  
  STDERR stderr;  
  ODS OUTPUT ParameterEstimates=LSM_MIAN;  
run;
```

The following statistics will be displayed :

- n (number of values analyzed) and nimp (number of imputed values)
- LS Means of each treatment group (including SE and 95% CI)
- LS Mean treatment difference (including SE, 95% CI, and p-value).

All results from the above-described sensitivity analyses, including any CIs and p-values provided, will be interpreted descriptively only.

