The results of a previous study [4] suggest that a treatment effect of about one standard deviation might be expected. For a 5% type I error and a randomization ratio of 2:1 a total sample size of 51 analyzable subjects is required to achieve 90% power. In order to account for uncertainty in parameter estimates and drop-outs it has been decided to randomize approximately 75 subjects.

6 Changes in the Planned Analyses

Compared to CSP version 3.0 dated 31-May-2021 and amendment 1 to CSP version 3.0 dated 26-MAY-2023, the following change to planned analyses is included in this SAP:

Sections [2.2.1.2.2](#) and [2.2.1.3](#):

- For precision, “as assessed by the investigator” was added to the definition of all other secondary endpoints and all other efficacy endpoints that are based on the TETRAS performance assessments in the bilateral treatment period. In accordance with the CSP, the IRP did not perform any assessments in Cycle 2.

Section [2.2.1.3](#):

- In the definition of other efficacy endpoints for the bilateral treatment period (Cycle 2) based on angular tremor amplitude assessments, the word “difference” was missing in the CSP and therefore added in part c) of the definition before “between both ULs”.
- The following restriction was added to definition of other efficacy endpoints for the bilateral treatment period (Cycle 2) based on angular tremor amplitude assessments:
“Changes from study baseline are only analyzed for motor-dominant UL because, in accordance with the visit schedules for treatment Cycles 1 and 2 in the CSP (see Tables 5 and 6), angular tremor amplitude of motor-dominant UL was only assessed in Cycle 2.”

Section 3:

- In the definition of the FAS-UP, “study baseline (V2)” was changed to “study baseline” and in the definition of the FAS-BP, “Cycle 2 baseline visit (V8)” was changed to “Cycle 2 baseline”.

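### Minor coding errors in the multiple-imputation sensitivity analysis: age is missing from the variable list, imputed amplitudes are rounded to whole degrees, and the pooling step has no small-sample degrees of freedom

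*SAP*

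**What the plan says.** SAP 4.1.1.2, no. 4, applies when more than 10% of treated subjects in either arm lack the primary endpoint. It creates 1000 completed datasets, fits the primary ANCOVA to each and pools the results.

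- **Predictors.** Protocol 12.4.1.1 and the SAP text list earlier amplitudes, treatment, site, gender and age. The code has explicit models for baseline and Week 4 that include age, the latter being "FCS REG(V3VAL = TRT01P SITEID SEX AGE BASE". The variable list is "VAR TRT01P SITEID SEX BASE V3VAL AVAL". Week 6 (AVAL) has no explicit model.
- **Rounding.** MINIMUM and ROUND each have six entries. The last three (0 and 1 respectively) fall on BASE, V3VAL and AVAL. SAP 4.1.1.1 derives the observed amplitude as a mean over rounds, "separately for each task (rounded by five decimal places".
- **Pooling.** The pooling code starts with "PROC MIANALYZE data=diff_mi" and gives only the estimate and its standard error. The ANCOVA being pooled uses Kenward-Roger degrees of freedom (SAP 4.1.1.1), and for that model "The two-sided t-test of the LS Mean treatment difference will be applied".

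Both code blocks are offered as approximate. All sensitivity results are to be read descriptively.

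**The concern.** Sensitivity analyses 1 to 3 (per-protocol set, site interaction, added covariates) do not address missing data, so no. 4 is the only planned check on it for the primary endpoint. Missingness is possible because the derivation rule is strict. Under SAP 4.1.1.1, one absent value among 4 tasks × 3 rounds × 3 axes = 36 at baseline, or among 3 rounds × 3 axes = 9 at Week 6, makes the endpoint missing.

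A programmer who follows the template would either meet an error or fit an imputation model other than the one promised. Observed and imputed values of different precision would be mixed in one endpoint. The pooled interval would also rest on a near-normal reference distribution, although the model being pooled uses small-sample degrees of freedom. At stake is how faithful and precise one supporting analysis is, not the trial's main conclusion.

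**Working it through.** Analysis no. 4 contains no numerical result to reproduce. The one recomputable design figure, 51 analysable subjects, is not in dispute and does reproduce: a two-sample t-test with 34 + 17 subjects, a 1 SD effect and two-sided 5% has power 0.910 (48 subjects give 0.892).

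**1. Age.** The variable list has six names: treatment, site, sex, baseline, Week 4, Week 6. MINIMUM and ROUND have six slots each, so none is left for age. Yet age is in the text and in two model statements. Under usual PROC MI behaviour (an assumption about the software), a variable outside VAR either stops the step or is not available to it, and a variable without its own model is imputed from the VAR variables only. Week 6 would then be imputed from treatment, site, sex, baseline and Week 4, without age. The documents give no association between age and amplitude, so no size can be computed.

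**2. Rounding.** Rounding to the nearest 1 degree adds an error that is roughly uniform on ±0.5, with variance 1/12 = 0.083 deg² and SD 0.289 deg. Relative to an amplitude SD of s, the added variance per imputed value is 0.083/s². The documents give no SD in degrees, so s is assumed:

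| s (deg) | Added variance per imputed value |
|---|---|
| 0.5 | 33% |
| 1 | 8.3% |
| 2 | 2.1% |
| 4 | 0.5% |

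Over the whole sample the effect is diluted. With 12% of values imputed (illustrative) and s = 1, it is 0.12 × 8.3% = 1.0%. If baseline is missing, footnote 10 of the SAP requires Week 6 to be imputed as well, so that subject's change score carries about 2 × 0.083 = 0.167 deg².

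**3. Degrees of freedom.** Let m = 1000 and let λ be the share of total variance due to missing data.

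- Rubin, no complete-data df: ν_R = (m − 1)/λ². At λ = 0.05 this is 999/0.0025 = 399,600; at λ = 0.30 it is 999/0.09 = 11,100. The critical value is 1.960 in both cases.
- Barnard-Rubin, complete-data df ν: ν_obs = [(ν + 1)/(ν + 3)] × ν × (1 − λ), and pooled df = 1/(1/ν_R + 1/ν_obs).
- Upper case for ν: 75 subjects − intercept − treatment − baseline − 14 site terms (about 15 sites) = 58. The lower values 40 and 30 are assumed, to allow for arm-specific variances and a placebo arm of about 25.

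| ν | λ | Pooled df | t(0.975) | Correct CI wider by |
|---|---|---|---|---|
| 58 | 0.05 | 53.3 | 2.005 | 2.3% |
| 58 | 0.30 | 39.1 | 2.022 | 3.2% |
| 40 | 0.05 | 36.2 | 2.028 | 3.5% |
| 40 | 0.30 | 26.6 | 2.053 | 4.7% |
| 30 | 0.05 | 26.8 | 2.053 | 4.7% |
| 30 | 0.30 | 19.7 | 2.088 | 6.5% |

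Example for the first row: (59/61) × 58 × 0.95 = 53.3, and 2.005/1.960 = 1.023.

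**The case against.** The best defence is that the code is illustrative, the governing sentence lists age correctly, and SAP 1.1 provides for quality control of the programming. If age outside the list halts the program, the slip is found and cannot distort a result. The analysis is conditional and descriptive. SAP 4.1.2.1 also reports that both key secondary endpoints were complete for all treated subjects at the blinded review. One of them is an on-site investigator rating at Week 6, so missing or incomplete kinematic recordings are probably the main route to missing data. All of this stands and limits the impact. It does not make the template correct, and the SAP does not say that imputation was found unnecessary for the primary endpoint.

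Three stronger readings are tempting but not supported:

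- **That the code contradicts its text throughout.** Only age is such a contradiction. The text of no. 4 is silent on rounding, where the mismatch is with the derivation in 4.1.1.1. It is also silent on pooled degrees of freedom, which is an omission.
- **That the missing Week 6 model is a separate error.** It is largely the same slip. Once age is in the list, the default model for Week 6 would include it, along with baseline and Week 4 as footnote 12 requires.
- **That the faults favour NT 201.** Rounding adds noise, which tends to widen the interval, while the missing degrees of freedom narrow it. No net direction is shown. Rounding could shift means if amplitudes were well below 1 degree, but nothing in the documents shows that they are.

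**Conclusion.** The point holds as a minor one. The template omits age from the variable list despite the stated model, with an effect that cannot be computed. It coarsens imputed amplitudes to whole degrees: about 8% extra variance per imputed value if the SD is 1 degree, about 2% or less at 2 degrees or more. It also gives a pooled interval that should be about 2–3% wider at 58 complete-data degrees of freedom and about 5–6% wider at 30.

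These sizes rest on assumed values for the amplitude SD, for λ (0.05 to 0.30) and for the lower degrees of freedom. They also rest on standard SAS behaviour for variables outside VAR and for PROC MIANALYZE without EDF=; the documents state neither. A reader might infer that the primary result is at risk. It is not, because the confirmatory ANCOVA replaces no missing values and does not use this code. The documents do not say whether the 10% trigger was met.

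**What to change.** Amend the template in SAP 4.1.1.2, no. 4:

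1. Use `VAR TRT01P SITEID SEX AGE BASE V3VAL AVAL` and add a fourth `.` slot to MINIMUM (and to ROUND, if kept) so that the positions still match.
2. For clarity, add `FCS REG(AVAL = TRT01P SITEID SEX AGE BASE V3VAL)`.
3. Delete ROUND, or set its three amplitude slots to 0.00001.
4. Supply `EDF=` in each PROC MIANALYZE call under a rule fixed in advance. Kenward-Roger values differ by contrast and between completed datasets, so the rule should say which is used, for example the mean or the minimum for the relevant contrast across the 1000 datasets.

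The cost is a few lines of SAS and one sentence of text. No new data are needed, and neither the primary analysis nor the sample size changes.
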